13.5 Vital Signs

Vital signs (systolic and diastolic blood pressure [SBP and DBP], pulse rate, and body temperature) will be summarized using descriptive statistics at baseline and at each post-baseline time point. Changes from baseline will also be summarized.

Vital sign values in adults (≥ 18 yrs) will be classified as normal, low, high, based on reference ranges as per below. Subjects with markedly abnormal changes will be listed and tabulated separately.

	Absolute Values			Change (Absolute) from Baseline	
	Low	Normal	High	Abnormal Change	Markedly Abnormal Change
SBP	<90 mmHg	90-140 mmHg	>140 mmHg	≥ 20 mmHg	≥ 40 mmHg
DBP	<50 mmHg	50-90 mmHg	>90 mmHg	≥ 10 mmHg	≥ 20 mmHg
Pulse	<50 bpm	50-100 bpm	>100 bpm	≥ 10 bpm	≥ 30 bpm

Blood pressure in children (<18 yrs) will be classified as normal or elevated based on reference ranges as per Table below. Subjects with markedly abnormal changes will be listed and tabulated separately.

		Absolute Values		Change (Absolute) from Baseline	
Age		Normal	Elevated	Abnormal Change	Markedly Abnormal Change
2-6 yrs old	SBP	<105 mmHg	≥ 105 mmHg	≥ 20 mmHg	≥ 30 mmHg
	DBP	<67 mmHg	≥ 67 mmHg	≥ 10 mmHg	≥ 20 mmHg
7-11 yrs old	SBP	<110 mmHg	≥ 110 mmHg	≥ 20 mmHg	≥ 30 mmHg
	DBP	<74 mmHg	≥ 74 mmHg	≥ 10 mmHg	≥ 20 mmHg
12-17 yrs old	SBP	<120 mmHg	≥ 120 mmHg	≥ 20 mmHg	≥ 30 mmHg
	DBP	<80 mmHg	≥ 80 mmHg	≥ 10 mmHg	≥ 20 mmHg

Pulse in children (<18 yrs) will be classified as low, normal, or high based on reference ranges as per Table below. Subjects with abnormal (low or high) values will be listed and tabulated separately.

[figure not shown]
	Absolute Values		
	Low	Normal	High
2-10 yrs old	<60 bpm	60-140 bpm	>140 bpm
11-17 yrs old	<50 bpm	50-100 bpm	>100 bpm

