10.4.3 Safety Analyses

The ITT Population will be used in the analysis of safety data. Summaries will be presented overall and by the following categories: received tapinarof treatment in either DMVT-505-3101 or DMVT-505-3102; received vehicle treatment in either DMVT-505-3101 or DMVT-505-3102; received tapinarof treatment in DMVT-505-2104; and enrolled directly into DMVT-505-3103.

The number and percent of subjects with TEAEs will be summarized by system organ class, and preferred term for all TEAEs, all TEAEs considered by the Investigator to be related to study drug, all SAEs, all TEAEs leading to study drug discontinuation, and all TEAEs leading to study discontinuation. TEAEs will be defined as follows:

- For rollover subjects, all AEs reported in DMVT-505-3103 will be considered to be a TEAE except for those AEs ongoing at the end of the parent study (DMVT-505-3101, DMVT-505-3102, or DMVT-505-2104) but resolved prior to the Visit 1 date in DMVT-505-3103.
- For subjects enrolled directly into DMVT-505-3103, all AEs that start after the first dose of study medication will be considered to be a TEAE.

Data listings will be provided for subjects who discontinued the study due to an AE and for subjects with an SAE.

Laboratory values will be classified as normal, low or high based on normal ranges supplied by the laboratory. Changes from Baseline in abnormality status will be summarized using shift tables. For quantitative laboratory measures, observed values and changes from Baseline will be summarized descriptively by visit.

Observed vital sign values (systolic and diastolic blood pressure, pulse rate, and body temperature) and change from Baseline in vital signs will be summarized similarly to the laboratory values.

LTS scores will be summarized by visit for subject (or caregiver) overall assessment and Investigator overall assessment separately.

• [REDACTED]
[REDACTED]
[REDACTED]
[REDACTED]
[REDACTED]
[REDACTED]
10.4.5 [REDACTED]
[REDACTED].

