13.4 Clinical Laboratory Evaluation

All clinical laboratory (hematology, clinical chemistry, and urinalysis) values will be listed by treatment group and subject. The reference normal ranges and reference range indicators (e.g., high, low, normal) will be supplied by the central laboratory and displayed in the data listings. Values outside the normal range for chemistry and hematology laboratory parameters will be

flagged. Change from baseline in abnormality status will be summarized using shift tables by visit. For quantitative measures, observed values and change from baseline in clinical laboratory values will be summarized descriptively by visit.

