14. CHANGES TO PROTOCOL-SPECIFIED ANALYSES

Not applicable. There are no changes to the protocol-specific analyses.

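### SAP 13.5 classifies vital signs but plans no shift from baseline class, and its pediatric-pulse table counts children who were already abnormal at entry

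*SAP*

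**What the plan says.** Protocol 10.4.3 describes the laboratory analysis in three steps.

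- Classification: "Laboratory values will be classified as normal, low or high based on normal ranges supplied by the laboratory".
- Change of class: "Changes from Baseline in abnormality status will be summarized using shift tables".
- Quantitative summary: "For quantitative laboratory measures, observed values and changes from Baseline will be summarized descriptively by visit".

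It then turns to blood pressure, pulse and temperature, and says that observed values and "change from Baseline in vital signs will be summarized similarly to the laboratory values".

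SAP 13.4 carries the laboratory shift tables over: "Change from baseline in abnormality status will be summarized using shift tables by visit". SAP 13.5 gives descriptive statistics for vital signs at baseline and at each later time point, and adds "Changes from baseline will also be summarized". It then defines classes for adult SBP, DBP and pulse, for pediatric SBP and DBP in three age bands, and for pediatric pulse in two. For adults and for pediatric blood pressure, the separate listing and table are of markedly abnormal changes from baseline. For pediatric pulse the rule is different: "Subjects with abnormal (low or high) values will be listed and tabulated separately". SAP 13.5 mentions no shift table. SAP 14 states: "There are no changes to the protocol-specific analyses".

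**The concern.** Change from baseline in vital signs is one of the endpoints listed in the protocol synopsis, and the study has a single arm. With no control group, a subject's own baseline is the only internal reference for an abnormal reading. A reader of the safety tables will want to know how many subjects were normal at entry and became low, high or elevated on study.

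The SAP sets up the classes needed to answer that but plans no table that does. In the pediatric-pulse table a child who entered with an abnormal pulse looks the same as one who developed it. This bears on the interim safety review, which is triggered by pediatric exposure and for which all summaries are to be produced (SAP 10.5).

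**Working it through.** The plan states no figure to reproduce. The check sets the rules side by side and applies their own limits to simple cases.

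**Inputs (SAP 13.4 and 13.5)**

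| Rule set | Class limits | What is tabulated separately | Shift from baseline class |
|---|---|---|---|
| Adult SBP, DBP | normal 90-140 and 50-90 mmHg | change of at least 40 (SBP) or 20 (DBP) | none |
| Adult pulse | normal 50-100 bpm | change of at least 30 | none |
| Pediatric SBP, DBP | elevated from 105/67, 110/74 or 120/80 mmHg, by age band | change of at least 30 (SBP) or 20 (DBP) | none |
| Pediatric pulse | normal 60-140 bpm (2-10 years), 50-100 bpm (11-17 years) | any low or high value | none |
| Laboratory values | central laboratory ranges | not applicable | by visit |

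**Step 1. A reading that is abnormal at baseline and does not change**

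- Adult SBP 150 to 150: High, change 0 < 40, not tabulated.
- Adult pulse 105 to 105: High, change 0 < 30, not tabulated.
- Child aged 8, SBP 115 to 115: Elevated (at least 110), change 0 < 30, not tabulated.
- Child aged 8, pulse 145 to 145: High (above 140), tabulated.

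Pre-existing abnormality is therefore counted under 1 of the 4 vital-sign rule sets. In that table, a child who goes from 140 (Normal) to 145 (High) cannot be told apart from the child steady at 145.

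**Step 2. Do the change tables show movement out of the normal range?**

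- Adult SBP 138 to 177: Normal to High, change 177 - 138 = 39 < 40, not in the marked-change table. It meets the lesser abnormal-change limit of 20, but SAP 13.5 names only marked changes for separate tabulation.
- Adult DBP 60 to 80: Normal to Normal, change 80 - 60 = 20, in the marked-change table.

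The change limits and the class limits answer different questions. A marked change need not leave the normal range, and a move out of range need not be a marked change.

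**Step 3. Could simple class counts fill the gap?**

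SAP 13.5 does not say how the classes are displayed. Suppose the general rule for categorical variables in SAP 6 is applied, so that counts appear at baseline and at each visit. With *n* subjects observed at both times, *b* High at baseline and *v* High at the visit, the number newly High lies anywhere from max(0, *v* - *b*) to min(*v*, *n* - *b*). If *b* = *v*, this runs from 0 to min(*v*, *n* - *v*). Separate counts do not identify the number. The cross-classification does.

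**The case against.** **The protocol may not ask for shift tables here.** Its vital-sign sentence is about observed values and change from baseline, and so echoes the quantitative laboratory sentence just before it. The laboratory classes rest on ranges that the laboratory supplies, and the protocol gives no ranges for vital signs. On that reading SAP 13.5 delivers what was asked and SAP 14 is correct. This stands. A reader might infer that the SAP contradicts the protocol, but the text does not establish that. The wider reading is reasonable, and more so because the SAP itself adopts abnormality classes, but it remains an inference.

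**The blood-pressure and adult-pulse tables refer to baseline.** This also stands. A reader might infer that pre-existing high blood pressure is counted as an on-study abnormality. Step 1 shows that the planned tables do not do so.

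**Other outputs give some cover.** Subject data are listed, mean changes are summarized by visit, and a vital sign that worsens and is judged clinically significant is an adverse event under Protocol 8.1.1. These reduce the harm, but none gives the number of subjects who moved from normal to abnormal.

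**Shifts from this baseline have limits.** Under SAP 10.2 the baseline for rollover subjects is the last parent-study visit (Week 8 or Day 28), which is on treatment for those who had tapinarof. It is tempting to count only subjects who were normal at baseline. That would hide abnormalities that arose on tapinarof in the parent study, or that worsen within a class, so such an exclusion should not be made. Some shifts will also reflect measurement variability, and with no control arm this cannot be separated out.

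**Conclusion.** The point holds in a limited form. All four vital-sign rule sets lack a shift from baseline class. One of them, pediatric pulse, also counts abnormal values whatever the baseline. No planned summary table separates new from pre-existing abnormality.

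These statements rest only on the wording and limits in SAP 13.5. How many subjects are affected cannot be computed: the documents give no vital-sign means, variances or rates of abnormality at entry, and the share of counted children who were already abnormal could be anything from none to all. A figure built on assumed distributions would not be evidence about this trial.

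The analysis is descriptive and no test or decision rule depends on it, so the consequence is limited to how clearly the safety tables can be read. The change is still worth making, because it is nearly free and the study has no control arm to put abnormal readings in context.

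**What to change.** In SAP 13.5:

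1. Add shift tables of baseline class by class at each visit for SBP, DBP and pulse, within the existing adult and pediatric age bands. Keep a row for missing baseline, which SAP 10.2 allows, so that no subject drops out.
2. Split the pediatric-pulse table into children normal at baseline and children already low or high at baseline. Keep the existing total row.
3. Present both by the entry groups in SAP 7. Add a footnote that for subjects treated with tapinarof in a parent study the baseline is on treatment, so shifts show change during the extension only.

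All existing rows stay. The cost is a short SAP revision and a few more descriptive tables from data already collected. The downside is that some of the shifts shown will be measurement variability, which the text accompanying the tables should say.

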14. CHANGES TO PROTOCOL-SPECIFIED ANALYSES

Not applicable. There are no changes to the protocol-specific analyses.

16. APPENDICES

APPENDIX A: PRESENTATION OF DATA AND PROGRAMMING SPECIFICATIONS

[figure not shown]
General

- Specialized text styles, such as bold, italics, borders, shading, and superscripted and subscripted text will not be used in tables, figures, and data listings unless they add significant value to the table, figure, or data listing.
- Only standard keyboard characters are to be used in tables and data listings.
- Special characters, such as nonprintable control characters, printer-specific, or font-specific characters, will not be used on a table, figure, or data listing.
- Hexadecimal character representations are allowed (e.g., μ , α , β).
- All footnotes will be left justified and at the bottom of a page. Footnotes must be used sparingly and must add value to the table, figure, or data listing.

Tables

- Means and medians will be presented to 1 more decimal place than the raw data. Standard deviations will be presented to 2 more decimal places than the raw data. Minimums and maximums will be reported with the same number of decimal places as the raw data. If raw data has more than 2 decimal places, the same rule will be applied as the raw data with 2 decimal places.
- Percentages will be presented to the tenths place.
- For frequency counts of categorical variables, categories whose counts are zero will be displayed for the sake of completeness. For example, if none of the subjects discontinue due to “lost to follow-up,” this reason will be included in the table with a count of 0. Categories with zero counts will have zero percentages (i.e., 0.0%) displayed if the denominator of the percentage is greater than 0. Categories with zero counts will be displayed as ‘0’ without percentage if the denominator of the percentage is 0. Results of one hundred percent and zero percent will have the same decimal accuracy in tables as other percentages.
- Percentiles (e.g., 25%, 75%) must be presented to 1 decimal place more than the raw/derived data.
- The last footnotes will be
 - “Source: xxx”, where xxx indicates the source **table number(s)** if applicable (in case aggregated results like mean or median are plotted), or the source listing(s) (in case individual responses are plotted), and/or source dataset(s) (e.g., ADaM).
 - “PROGRAM SOURCE: ...\\xx.sas, DATA CUT-OFF DATE: DDMMYY YYYY, RUN DATE: DDMMYY hh:mm”.

Figures

- Legends will be used for all figures with more than 1 variable or item displayed.
- Figures will be in black and white but can be in color to add value to the clarity and readability of a figure. Lines must be wide enough to see the line after being copied.
- The last footnotes will be
 - “Source: xxx”, where xxx indicates the source listing number(s) and/or source dataset(s) (e.g., ADaM).
 - “PROGRAM SOURCE: ...\\xx.sas, DATA CUT-OFF DATE: DDMMYY YYYY, RUN DATE: DDMMYY hh:mm”.

Listings

[figure not shown]
- If not otherwise specified, all data listings will be sorted by sequence/treatment (pivotal/PK/direct enrolling), center, subject number, visit, and date/time, as appropriate.
- All date values will be presented in a SAS date (e.g., 29AUG2001) format.
- All observed time values will be presented using a 24-hour clock HH:MM:SS format (e.g., 01:35:45 or 11:26). Seconds will only be reported if they were measured as part of the study.
- The last footnote will be
 - “PROGRAM SOURCE: ...\\xx.sas, DATA CUT-OFF DATE: DDMMYY YYYY, RUN DATE: DDMMYY hh:mm”.

Standard Calculations

Variables requiring calculation will be derived using the following formulas:

- **Days** – A duration expressed in days between 1 date (date1) and another later date (date2) is calculated using the formulas noted below:
duration in days = date2 – date1 + 1
- **Months** – A duration expressed in months is calculated using the INTCK function of SAS as follows: months=intck('month','date1'd,date2'd, 'continuous').
- **Years** – A duration expressed in years between one date (date1) and another later date (date2) is calculated as follows:
duration in years = intck('year', 'date1'd, 'date2'd, 'continuous').
- **Age** – Age at time of informed consent will be reported on the CRF.
- **Height** – Height entries made in inches (in) are converted to centimeters (cm) using the following formula:
height (cm) = height (in) × 2.54.
- **Weight** – Weight entries made in pounds (lb) are converted to kilograms (kg) using the following formula:
weight (kg) = weight (lb)/2.2046.

- **Temperature** – Temperature entries in degrees Fahrenheit are converted to degrees centigrade using the following formula:
$$\text{temp (degrees centigrade)} = 5/9 \times [\text{temp (degrees Fahrenheit)} - 32].$$
- **Body Mass Index (BMI)** – BMI is calculated using height (cm) and weight (kg) using the following formula:
$$\text{BMI (kg/m}^2\text{)} = \text{weight (kg)}/[\text{height (cm)}/100]^2\text{].}$$
- **Change from baseline** – Change from baseline will be calculated as:
$$\text{Change} = \text{post-baseline value} - \text{baseline value}.$$
- **Percent change from baseline** – Percent change from baseline will be calculated as:
$$\text{Percent change from baseline} = (\text{post-baseline value} - \text{baseline value})/\text{baseline value} \times 100.$$

